9.6. Data Management

This study will be conducted in a distributed manner using a common protocol, common data model (CDM), and common analytics programs based on existing health data. The following steps will be implemented:

Extract Transform Load (ETL) of data to a CDM: To harmonise the structure of the datasets stored and maintained by each data partner, a shared syntactic foundation is used. The CDM that will be used has been developed within the IMI-ConcePTION project.⁵⁴ In this CDM, data are represented in a common structure, but the content of the data remain in their original format. The ETL design for each study is shared in a searchable FAIR catalogue. The VAC4EU FAIR data catalogue is a meta-data management tool designed to contain searchable meta-data describing organisations that can provide access to specific data sources. FAIR is defined as findable, accessible, interoperable, and re-usable. Data quality checks will be conducted to

measure the integrity of the ETL as well as internal consistency within the context of the CDM.

- 2. Second, to reconcile differences across terminologies, a shared semantic foundation is built for the definition of events of interest within a study by collecting relevant concepts in a structured fashion using a standardised event definition template. The Codemapper tool is used to create diagnosis code lists based on completed event definition templates for each outcome and comorbid risk condition based on the approach taken in the ACCESS project. Based on the relevant diagnostic medical codes and keywords, as well as other relevant concepts (e.g., medications), one or more algorithms are constructed (typically one sensitive, or broad, algorithm and one specific, or narrow, algorithm) to operationalise the identification and measurement of each event. These algorithms may differ by database, as the components involved in the study variables may differ. Specifications for both ETL and semantic harmonisation will be shared in the catalogue.
- 3. Third, following conversion to harmonised study variable sets, R programs for the calculation of incidence will be distributed to data access providers for local deployment. The aggregated results produced by these scripts will then be uploaded to the DRE for pooled analysis and visualisation (see Figure 4). The DRE is made available through UMCU/VAC4EU (https://www.andrea-consortium.org/). The DRE is a cloud-based, globally available research environment where data are stored and organised securely and where researchers can collaborate (https://www.andrea-consortium.org/azure-dre/).

[figure not shown]

Figure 4 Data Management Plan

9.6.1. Data Extraction

Each DAP will create ETL specifications using the standard ConcePTION ETL design template (accessible via this link:

https://docs.google.com/document/d/1SWi31tnNJL7u5jJLbBHmoZa7AvfcVaqX7jiXgL9uAW g/edit). Following completion of this template and review by study statisticians, each DAP will

PFIZER CONFIDENTIAL

CT24-WI-GL02-RF02 5.0 Non-Interventional Study Protocol Template For Secondary Data Collection Study 01-Aug-2023 Page 43 of 72 extract the relevant study data locally using their preferred software (e.g., Stata, SAS, R, Oracle). These data will be loaded into the CDM structure in csv format. These data remain local (see Figure 4).

9.6.2. Data Processing and Transformation

Data processing and transformation will be conducted using R code against the syntactically harmonized CDM. The R scripts will first transform the data in the syntactically harmonized CDM to semantically harmonized study variables (see Figure 4). Following creation of study variables, the data will be characterized. This characterisation will include calculation of code counts and incidence rates, as well as benchmarking within the data source (over time), between data sources and externally (against published estimates). Subsequently, R code to conduct study-specific statistical analysis against semantically harmonized study variables will be distributed and run locally to produce aggregated results. The R scripts for these processing and analysis steps will be developed and tested centrally and sent to the DAPs.

The R scripts are structured in modular form to ensure transparency. Functions to be used in the modules will be either standard R packages or packages specifically designed, developed, and tested for multi-database studies. Scripts will be double coded in R and quality checks will be thoroughly documented.

The DAPs will run the R code locally and send aggregated analysis results to the DRE using a secure file transfer protocol. In the DRE, results will be further plotted, inspected (for quality assessment), and pooled (if needed) for final reporting.

All final statistical computations will be performed on the DRE using R. Data access providers will have access to the workspace for script verification.

Aggregated results, ETL specifications, and a repository of study scripts will be stored in the DRE.

Within the DRE, each project-specific area consists of a separate secure folder called a 'workspace'. Each workspace is completely secure, and researchers are in full control of their data. Each workspace has its own list of users, which can be managed by its administrators.

The DRE architecture allows researchers to use a solution within the boundaries of data management rules and regulations. Although the General Data Protection Regulation (GDPR) and Good (Clinical) Research Practice still apply to researchers, the DRE offers tools to control and monitor which activities take place within projects.

All researchers who need access to the DRE are granted access to study-specific secure workspaces. Access to this workspace is only possible with double authentication using an identification code and password together with the user's mobile phone for authentication. Upload of files is possible for all researchers with access to the workspace within the DRE. Download of files is only possible after requesting and receiving permission from a workspace member with an 'owner' role.

9.7. Data Analysis

Detailed methodology for summary and statistical analyses of data collected in this study will be documented in a SAP, which will be dated, filed, and maintained by the sponsor and PI. The SAP may modify the plans outlined in the protocol; any major modifications of primary endpoint definitions or their analyses will be reflected in a protocol amendment. The SAP will also provide additional detail regarding the evaluation of a threshold of excess risk for each of the outcomes of interest. This will be determined based on background incidences for each event, in addition to prespecified significance level (e.g., alpha = 0.01 or 0.05) and power. All analyses will be conducted using R version R-4.0.3 or higher.⁵⁵

The SAP will contain additional detail of the data analysis and meta-analysis. One interim analysis and report may be conducted. The interim report will be limited to descriptive analyses. Comparative analyses will be included in the final report. Further details will be described in the SAP.

All analyses will be conducted separately for the 3 populations of interest: immunocompromised, renally impaired, or hepatically impaired; and if appropriate, in the combined population. Prior to any combined analysis, a Higgin's I2 statistic will be used to assess the heterogeneity in the primary outcomes across the 3 populations of interest. If the percentage of heterogeneity estimated by I2 is high (e.g., >50%; specific threshold to be specified in the SAP), a combined effect may be estimated using adapted methods such as a random-effects model.

9.7.1. Baseline Characteristics

Baseline demographics and clinical characteristics for individuals vaccinated with ABRYSVO and the unvaccinated cohort will be summarized using descriptive statistics, consisting of the mean, SD, median, inter-quartile range, minimum, and maximum values for continuous variables and frequency distributions for categorical variables. Descriptive statistics will also be used to summarize ABRYSVO uptake characteristics, including calendar year and month of vaccination and care setting of vaccination (e.g., outpatient clinic, pharmacy, inpatient ward if available).For the comparative cohort design analysis, crude standardized differences in the baseline characteristics will be calculated between vaccinated and unvaccinated cohorts before and after weighting. Standardized differences <10% will indicate that the baseline characteristics of ABRYSVO vaccinated and unvaccinated cohorts are balanced.

9.7.2. Incidence Rates of Outcomes

Incidence rates per 1,000 patient-years (and corresponding 95% CIs) will be calculated for prespecified outcomes (as described in Section 9.3.2) as the total number of incident events divided by the total observation time/person-time. The number of cases and incidence rates of each outcome will be reported for each of the populations of interest (i.e, immunocompromised, renally impaired, and hepatically impaired populations separately) in the vaccinated and unvaccinated cohorts.

For outcomes with unknown risk windows or those that require longer follow-up (e.g., death), the cumulative incidence will be computed, which will be estimated with a 1 - Kaplan-Meier survival curve, as well as with adjusted parametric incidence curves.⁵⁶ Time to outcome onset will be defined as the time from the index date until the occurrence of the prespecified outcome event or censoring. For most outcomes, the associated severity and rapidity of onset are likely to result in a healthcare encounter close to the time of outcome onset, so the date of onset will be assumed to be the date of the healthcare encounter. The SAP will elaborate on further analyses for outcomes that may have a time lag between symptom onset and a healthcare encounter (e.g., DVT, diabetes type 1).

For individuals without an outcome, the censoring date will be defined as the date of death, date of RSV vaccination (for unvaccinated individuals who later receive any RSV vaccine only), end of the administrative follow up, or the end of data availability, whichever occurs earliest. For outcomes with defined risk windows, censoring will also occur at the end of the risk window. For composite outcomes, follow-up will be censored at the date of the first occurrence of any of its components.

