9.2.4. Study Period

The study period will start from 23 August 2022 to allow at least 12 months of administrative enrolment before vaccination with vaccination possible from the date of approval in the EU. Data collection will extend through a minimum of three vaccination seasons (2023, 2024, and 2025). Patient follow-up will last for up to 12 months post-vaccination depending on the outcome; therefore, data collection will extend through the end of 2026, at a minimum. Vaccine uptake will be periodically monitored to inform the overall length of the study period, and additional vaccination seasons (with 12-month post-vaccination follow-up) may be added based on vaccine uptake and exposure accrual. Time lags for data availability will be taken into account for analysis and reporting purposes.

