9.3.2. Outcome Definitions

9.3.2.1. Safety Outcomes

Outcomes will be defined consistently across the data sources to the fullest extent possible.

Body system/ classification	Adverse event of special interest	Estimated risk window (days) ^a .	Analytic Approach
Autoimmune diseases	Acute disseminated encephalomyelitis	1-42 ^{39, b} .	Cohort/SCRI
	Diabetes mellitus type I	1-365	Cohort
	Guillain-Barré syndrome	1-42 ^{39, b} .	Cohort/SCRI
	Narcolepsy	1-365°.	Cohort
	Thrombocytopenia (idiopathic)	$1-42^{40}$	Cohort/SCRI
	Thrombosis thrombocytopenia syndrome	1-15 ³⁹	Cohort/SCRI
Cardiovascular system ^{d.}	Acute cardiovascular injury	$1-28^{41}$	Cohort
-	Arrhythmia Specific subgroups of patients with atrial fibrillation and supraventricular arrhythmias will be identified for additional analyses	1–365 ^{e. g.}	Cohort
	Coronary artery disease	1–365	Cohort

Table 1List of Select Adverse Events of Special Interest

PFIZER CONFIDENTIAL

CT24-WI-GL02-RF02 5.0 Non-Interventional Study Protocol Template For Secondary Data Collection Study 01-Aug-2023 Page 30 of 72

Body system/	Adverse event of special interest	Estimated risk	Analytic Approach	
classification		window (days) ^a .		
	Heart failure	1–365	Cohort	
	Microangiopathy	1–365	Cohort	
	Myocarditis	1-21	Cohort/SCRI	
	Myocarditis and pericarditis	1-7	Cohort/SCRI	
	Pericarditis	1-14	Cohort/SCRI	
	Stress cardiomyopathy	1-365	Cohort	
Cinculatory		1-303 $1-28^{39, f.}$	Cohort/SCRI	
Circulatory	Coagulation disorders: Disseminated intravascular	1-20	Conort/SCRI	
system				
	coagulation, venous			
	thromboembolism (pulmonary			
	embolism, deep vein thrombosis),			
	thrombotic microangiopathy,			
	cerebral venous thrombosis,			
	thrombotic thrombocytopenia			
	syndrome, ischemic stroke,			
	myocardial infarction, haemorrhage	-		
	Single organ cutaneous vasculitis	1-28 ^{f.}	Cohort/SCRI	
	Thrombocytopenia with venous	1–15	Cohort/SCRI	
	thromboembolism			
Nerves and	Bell's palsy	1-42 ³⁹	Cohort/SCRI	
central nervous	Generalised convulsion	0-42 ^{39, , g.}	Cohort/SCRI	
system	Meningoencephalitis	1-42 ³⁹	Cohort/SCRI	
	Transverse myelitis	1–42 ^{39, b. c.}	Cohort/SCRI	
Respiratory	Acute respiratory distress syndrome	1–365	Cohort	
system				
Skin and mucous	•	1–42	Cohort	
membrane, bone				
and joints system				
Other system	Anaphylaxis	0-1 ^{39, , g.}	Cohort/SCRI	
	Death (any causes)	0–365 ^{, g.}	Cohort	

Table 1 List of Select Adverse Events of Special Interest

Notes:

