			3	157	157		
			5	59	59		
			10	22	22		

Notes:

a. Due to a lack of published background incidence rates of outcomes of interest among the study-specific population (i.e., adults aged 60 and older who are immunocompromised or renally impaired or hepatically impaired), background rates of outcomes among adults aged 60 and older from general European populations ,published in Supplement 1, Table 1 of Willame et al (2023)⁵³ using VAC4EU databases were used as the basis of sample size and power calculations. A range of background rates were used to address potential differences in underlying rates between the general and study-specific populations (i.e., higher and lower background incidence rates of outcomes than were published in Willame et al.). Sample size and power calculations may be updated during the study as new and relevant background rate data emerges. Key study design features will be reviewed in the light of any updated sample size and power calculations.

b. Assuming a two-sided alpha = 0.05, power of 80%, and a ratio of 1:1 of vaccinated to unvaccinated. Examples of background IR accounting for the risk window:

Anaphylaxis (10/100,000 person-years)/365 * risk window (risk window 2 days) = 0.0000005

GBS (6/100,000 person-years)/365 * risk window (risk window 42 days) = 0.0000069

Arrhythmia (2,000/100,000 person-years)/365 * risk window (risk window 365 days) = 0.02

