Individuals will be followed from the index date until death, end of administrative follow up (and/or risk interval), end of the study period, or the date of ABRYSVO/RSV vaccination (for unvaccinated individuals who later receive any RSV vaccine only), whichever occurs first. The degree of loss to follow-up will be examined. If the censoring rates differ by exposure group (i.e, indicating informative censoring) and high censoring rates (e.g., >20%) are observed, IPCW will be derived to account for informative censoring, where the weight will be calculated for each individual as the inverse of the probability of remaining uncensored during the risk interval. The stabilized IPCW will be calculated as follows, where A= vaccination, V = covariates to adjust, and C=0 represents that the patient has remained uncensored: (Pr[C=0 | A=1])/(Pr[C=0 | A=1,V=v]) for the vaccinated cohort; (Pr[C=0 | A=0])/(Pr[C=0 | A=0,V=v]) for the unvaccinated cohort.

The final weights will be calculated as the product of the ATT weight and IPCW (ATT x IPCW) if informative censoring is observed, and the ATT weight will be used as the final weight if informative censoring is not observed. The distribution of final weights (e.g., mean, SD, minimum, and maximum values) will be examined and extreme weights will be truncated or capped at the 1st and 99th percentile. After weighting, the distribution of baseline characteristics will be evaluated between the vaccinated cohort and the unvaccinated cohort, and variables that remain inadequately balanced (standardized difference >10%) between the two cohorts will be included as regression model covariates in a doubly robust approach.

Weighted Poisson regression models will be conducted to calculate IRRs of outcomes among vaccinated cohort vs. unvaccinated cohort. Incidence rate ratios will be summarized, and robust variance estimators will be used to calculate the corresponding 95% CIs.

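### For non-fatal outcomes with long follow-up, 1 minus Kaplan-Meier with deaths censored overstates the proportion who have the event; this affects a supplementary absolute-risk display, not the rates or rate ratios

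*Protocol*

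**What the plan says.** Protocol Section 9.7.2 sets the scope: "For outcomes with unknown risk windows or those that require longer follow-up (e.g., death), the cumulative incidence will be computed". It then names the method: "which will be estimated with a 1 - Kaplan-Meier survival curve", with adjusted parametric curves as a second estimate. Two paragraphs later it gives the censoring rule: "For individuals without an outcome, the censoring date will be defined as the date of death", alongside later RSV vaccination of a comparator and the administrative end points.

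Section 9.7.3.1 treats death the same way for cohort follow-up: "Individuals will be followed from the index date until death, end of administrative follow up (and/or risk interval), end of the study period".

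Section 9.7.2 does not list the outcomes that get a cumulative incidence; death is its only example. Section 9.2.4 says "Patient follow-up will last for up to 12 months post-vaccination depending on the outcome". Table 1 in Section 9.3.2.1 gives windows of 1 to 365 days to type 1 diabetes, narcolepsy, arrhythmia, coronary artery disease, "Heart failure", microangiopathy, stress cardiomyopathy and acute respiratory distress syndrome. All-cause death has 0 to 365 days.

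The protocol nowhere mentions competing risks, a cumulative incidence function or the Aalen-Johansen estimator.

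**The concern.** Censoring assumes that a person who leaves observation could still have the event later, at the same rate as those who remain. Someone who has died cannot go on to develop heart failure. With deaths censored, 1 minus Kaplan-Meier therefore estimates the risk in a hypothetical setting without death, although it is labelled cumulative incidence and will be read as the proportion of people who have the event.

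The participants are 60 or older and include people with treated malignancy, transplant recipients and people with moderate or severe hepatic impairment. Mortality over a year may well not be negligible in some of these groups, although the protocol gives no figure. At stake is the accuracy of the one-year absolute risks shown for each cohort and each of the three populations. The overstatement grows with mortality, so it need not be the same across those groups.

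**Working it through.** **Inputs from the protocol.** Arrhythmia background rates of 2,000 and 5,000 per 100,000 person-years (Section 9.5, Table 2). The lower is converted as "Arrhythmia (2,000/100,000 person-years)/365 * risk window (risk window 365 days) = 0.02", so the annual event hazards are λ = 0.02 and λ = 0.05.

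**Input not in the protocol.** Mortality. One-year mortality m from 2% to 40% is assumed, with death hazard μ = -ln(1 - m).

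**The plan's own figure first.** The protocol states no cumulative incidence. The nearest figure using the same event rate is the arrhythmia sample size for a rate ratio of 2:

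n per cohort = (1.960 + 0.842)² × (1 + 2) / (0.02 × (2 - 1)²) = 7.849 × 3 / 0.02 ≈ 1,177.3, rounded up to 1,178.

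This matches Table 2, so the event rate is read as the protocol intends.

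**Direction, without assumptions about rates.** Let dΛ(u) be the increment of the cause-specific event hazard at time u.

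- 1 minus Kaplan-Meier with deaths censored sums S₁(u-) dΛ(u), where S₁ is reduced by events only.
- Aalen-Johansen sums S(u-) dΛ(u), where S is reduced by events and by deaths.

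Since S ≤ S₁ at every time, the first sum is never below the second. They agree only if no deaths precede events. When the outcome is death itself there is no competing event and 1 minus Kaplan-Meier is correct.

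**Size, with constant hazards over one year.**

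- 1 minus Kaplan-Meier: 1 - exp(-λ)
- Cumulative incidence with death competing: λ/(λ + μ) × [1 - exp(-(λ + μ))]

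| Assumed one-year mortality | λ = 0.02: 1 - KM | λ = 0.02: death competing | λ = 0.05: 1 - KM | λ = 0.05: death competing | Relative excess at λ = 0.05 |
|---|---|---|---|---|---|
| 2% | 1.98% | 1.96% | 4.88% | 4.83% | 1.0% |
| 5% | 1.98% | 1.93% | 4.88% | 4.76% | 2.6% |
| 10% | 1.98% | 1.88% | 4.88% | 4.63% | 5.3% |
| 20% | 1.98% | 1.78% | 4.88% | 4.38% | 11.5% |
| 30% | 1.98% | 1.67% | 4.88% | 4.11% | 18.7% |
| 40% | 1.98% | 1.55% | 4.88% | 3.83% | 27.4% |

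The relative excess is almost the same at λ = 0.02. The absolute excess runs from 0.02 to 0.43 percentage points at λ = 0.02 and from 0.05 to 1.05 points at λ = 0.05.

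**One line in full.** With λ = 0.05 and an assumed μ = 0.20 per year (one-year mortality 1 - exp(-0.20) = 18.1%): 1 - exp(-0.05) = 4.88%, against 0.05/0.25 × [1 - exp(-0.25)] = 0.2 × 0.2212 = 4.42%.

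**Unequal mortality, equal event hazards.** With λ = 0.05 in both cohorts and assumed one-year mortality of 10% and 20%, 1 minus Kaplan-Meier gives 4.88% in each. The proportions who have the event are 4.63% and 4.38%, a ratio of 1.06.

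**Does anything else in the protocol repair this?** The case-fatality rule and Farrington adjustment in Section 9.7.3.2 apply only to the self-controlled design. Inverse probability of censoring weighting in Section 9.7.3.1 is used only when censoring is both high and different between cohorts, and it is described for the weighted Poisson comparison. Weighting deaths away would again target risk in the absence of death, so it would not recover the observed proportion.

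**The case against.** The strongest counter-argument is that this is a side display. The objective in Section 8.2 is incidence rates and rate ratios, and Section 9.7.2 opens with rates per 1,000 patient-years and confidence intervals for every outcome. With person-time ended at death, those rates and the Poisson rate ratios are valid cause-specific measures. This stands. A reader might infer that the main comparative results are biased, or that these curves are the study's only absolute measure; the documents support neither.

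A reader might also infer that misleading risk differences will be reported. Sections 9.7.3 and 9.7.3.1 compare rates, and no difference in cumulative incidence is planned.

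The list of affected outcomes is an inference. Section 9.7.2 names only death, for which the method is correct. But its wording covers a class of outcomes of which death is an example, and the 365-day windows in Table 1 make non-fatal members of that class the natural reading.

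Materiality is uncertain. No mortality figure is given, and the populations also include people with eGFR below 60 or treated inflammatory disease. Overstatement above 10% needs one-year mortality near 20%, and outcomes rarer than arrhythmia would show smaller absolute gaps.

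The unequal-mortality example assumes a mortality gap between cohorts that are to be weighted for comparability, and all-cause death is itself reported. It can also be argued that equal curves are the better display there, since the event hazards are equal. For an aetiological comparison that is a fair choice of estimand, and the rate ratio already serves it. It does not make the curve a correct estimate of the proportion affected.

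Finally, the protocol text does not show how the adjusted parametric curves handle death. It would be wrong to infer that they share the error.

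**Conclusion.** Wrong as written, in a limited part of the plan. Section 9.7.2 fixes both the estimator and the censoring of deaths, so this is not a detail left open for the SAP. Followed literally, it gives cumulative incidences for non-fatal outcomes that cannot be too low relative to the competing-risk estimate and will generally be too high.

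The direction is certain. The size rests on assumed mortality and constant hazards: about 1% to 3% relative at one-year mortality of 2% to 5%, and about 11% to 27% at 20% to 40%. Which outcomes are affected is inferred from Table 1. The incidence rates, the incidence rate ratios and the cumulative incidence of all-cause death are unaffected.

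**What to change.** In Section 9.7.2, state that for every non-fatal outcome the cumulative incidence will be estimated with the Aalen-Johansen estimator, with death as a competing event and not a censoring event for that estimate. Keep 1 minus Kaplan-Meier for all-cause death only. Leave death as the end of person-time for rates and Poisson models. Name the outcomes that will get a cumulative incidence, and state that any adjusted parametric curve shown beside it must target the same quantity.

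No new data are needed, because death is already an outcome and an end of follow-up. The cost is a little more programming, run in five data sources and double-coded, and slightly lower reported absolute risks.
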